9.3 Sample Size/Accrual Rate

The accrual goal is three participants. This is an appropriate sample size for the study objectives, since this preliminary investigation will not attempt to definitively determine the safety or efficacy of this treatment.

10.0 HUMAN PARTICIPANTS PROTECTION

10.1 Equitability

Accrual will be equitable among patients with VHL disease meeting the enrollment criteria for this study.

10.1.1 Justification for Exclusion of Children

Children are not eligible for this study, as the safety of E10030 and ranibizumab has not been investigated in children. Furthermore, it is unlikely that young participants will be able to comply with all examinations and with intravitreal injections.

10.1.2 Justification for Exclusion of Pregnant or Lactating Women

Women who are pregnant or breastfeeding are excluded from this study because of the unknown risks of E10030 or ranibizumab on a fetus or nursing baby and the uncertainty with respect to whether E10030 or ranibizumab is excreted in human milk. Given the known and unknown effects on pregnancy outcomes, two forms of contraception will be required for female participants of childbearing potential (see Appendix 1 for definition). In addition, female participants of childbearing potential will undergo pregnancy tests throughout the study.

10.1.3 Justification for Exclusion of Individuals without Consent Capacity

Vulnerable subjects who lack consent capacity or are cognitively impaired are excluded from this study because they are frequently unable to cooperate with evaluation and testing in the manner standardized for other adult participants.

11.0 BENEFITS

Participants may benefit directly from this study if combined E10030 and ranibizumab treatment causes regression of RCH and preserves visual acuity. The study will also lead to generalizable knowledge that will enhance our understanding of using E10030 and ranibizumab as treatment for patients with RCH associated with VHL.

12.0 SUMMARY/CLASSIFICATION OF RISK

Risk is classified as more than minimal risk. The risks will be minimized with careful monitoring and are reasonable given that the participants are experiencing or are at risk of experiencing visual loss due to VHL disease.

13.0 CONSENT DOCUMENTS AND PROCESS

Study investigators with consenting privileges will obtain informed consent. All NIH study investigators obtaining informed consent have completed the National Institute of Mental Health (NIMH) Human Subject's Protection Unit (HSPU) "Elements of Successful Informed Consent" training. All participants will receive a verbal explanation in terms suited to their comprehension of the purposes, procedures and potential risks of the study. The participants must have the ability to understand and sign an informed consent form, which must be signed prior to enrollment. The participants will have an opportunity to carefully review the consent and ask questions regarding this study prior to signing, and they will be informed that they may withdraw from the study at any time without prejudice to themselves.

If the participant requires the consent to be in larger font in order to read it well, this will be provided. If participants are visually impaired to the point of being unable to read the consent, they can take the consent back with them to read it over with a family member or with the use of magnifying devices. If the participant chooses, the investigator can also read the consent verbatim to the participant and answer any questions that may arise.

An investigator present during the consent process will document the consent process in the participant's medical record. A copy of the signed informed consent form will be provided to the participant to take home.

13.1 Unanticipated Enrollment of Non-English Speaking Participants

If a non-English speaking participant is eligible for enrollment, the participant will be provided with the Clinical Center (CC) Short Written Consent Form for Non-English Speaking Research Subjects in the participant's native language and a verbal explanation of the purpose, procedures and risks of the study. The IRB-approved English consent form will serve as basis for the verbal explanation of the study. The investigator will obtain an interpreter unless the investigator is fluent in the prospective participant's language. Preferably, the interpreter will be someone who is not related to the participant (i.e., not a family member). Interpreters provided by the CC will be used whenever possible. The interpreters will interpret the IRB-approved English consent form and facilitate discussion between the participant and investigator.

The IRB-approved English consent form will be signed by the investigator obtaining consent and a witness to the oral presentation. The CC Short Written Consent Form will be signed by the participant and a witness who observed the presentation of information. The interpreter may sign the consent documents as the witness and, in this case, will note "Interpreter" with his/her signature. If not also serving as the witness, the interpreter will be separately identified on the short form in the space provided. A copy of both signed forms (the long form serving as the script and the short form) will be provided to the participant. The short form process, including the use of an interpreter, will be documented in the medical record in accordance with NIH policy.

All instances of use of the CC Short Written Consent Form will be reported to the IRB at the time of annual review. If the CC Short Written Consent Form is used three times or more for the same language within an IRB approval period, this will be reported to the IRB immediately.

Interpreters will also be present for other protocol procedures as necessary.

14.0 DATA AND SAFETY MONITORING

The NEI SAE Review Committee is responsible for monitoring data and safety, and will exercise oversight of the clinical investigation independently from the study investigators.

14.1 Coordinating Center

The Emmes Corporation (Emmes) has been assigned as the Coordinating Center for this trial to conduct data collection, protocol monitoring, data analysis and reporting. The Coordinating Center provides routine monitoring of study participants' data. More frequent monitoring visits will be performed at the beginning of the study when enrollment is open. Monitoring will decrease as enrollment closes and as participant follow-up continues.

Although the Coordinating Center advises the NEI CD and PI on data and statistical activities, the Coordinating Center staff does not have direct access to or interaction with participants.

14.2 NEI Serious Adverse Event Review Committee

The NEI SAE Review Committee, which consists of the NEI CD and three other NEI physicians, will be responsible for reviewing any reported serious safety events, if they occur under this protocol. The Committee will review data on a semiannual basis to determine whether the study should continue. If changes to the protocol are indicated, recommendations will be made to the NEI CD and Institutional Review Board (IRB) who will consider and act on such recommendations in a timely manner. Should any suspected serious adverse reactions occur, the NEI CD may, at his discretion, assemble the Committee before the scheduled date to consider if the study should go forward. In addition, if three or more participants experience non-serious suspected adverse reactions that require temporary or permanent cessation of the combination investigational treatment, the PI shall report this to the NEI CD. The NEI CD may convene the Committee before the scheduled time to consider the cessation of the study as a whole.

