3.0 PARTICIPANTS

Three participants with severe ocular VHL disease who meet the eligibility criteria will receive the combination investigational treatment in one eye and will be followed for 104 weeks. Inclusion and exclusion criteria are listed below.

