4.1 Recruitment

Most of the participants for this study can be recruited from the current patient population with ocular VHL disease at the National Eye Institute (NEI) and other institutes within NIH, including the National Institute of Neurologic Disorders and Stroke (NINDS) and the National Cancer Institute (NCI). The study may also rely on referrals from outside physicians at Kaiser Permanente, the support group of the VHL Alliance and other national clinical sites. If any recruitment materials are used, IRB-approval will be obtained prior to distribution. It is anticipated that all participants will be recruited within 12 months of activation.

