4.3 Study Design

This study will examine the effect of multiple E10030 and ranibizumab injections in participants with severe ocular VHL disease. A single study eye in each participant will receive combination treatment consisting of intravitreal injections of E10030 (1.5 mg in 0.05 mL) and ranibizumab (0.5 mg in 0.05 mL) (given as separate injections during the same procedure, meaning that participants will receive two intravitreal injections per visit, see Appendix 3) every four weeks from baseline through Week 16 (totaling five treatments) and then every eight weeks through Week 48 (totaling nine treatments from baseline). The primary endpoint will be assessed by tabulation of AEs reported through Week 52. During the second year, all participants will be seen at Weeks 60, 72, 84 and 104. Starting after Week 52, participants may return for additional visits

in the second year of the trial, as often as every four weeks, for evaluation and for administration of standard of care therapies, at investigator discretion. No further administration of investigational product will occur after the Week 48 visit. Participants will have a minimum of 14 study visits at the NEI outpatient clinic. The baseline study visit will require approximately five hours, and the subsequent visits will require approximately three to four hours each.

Standard of care therapies will be considered for significant clinical worsening at any time during the study, for clinical improvement starting at Week 16 (as in a case where clinical improvement makes an eye more amenable to ablative or surgical treatment), and without restriction starting at Week 40 (in anticipation of unavailability of investigational product after Week 48). Any participants who discontinue combination investigational treatment will be asked to return for all study visits and will be included in the analyses at the end of the study.

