#### **3.3** Study Population

Three participants with severe ocular VHL disease who meet the eligibility criteria will receive the combination investigational treatment in one eye and will be followed for 104 weeks. Inclusion and exclusion criteria are listed below.

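### The Section 14.2 reporting trigger for non-serious treatment-stopping reactions needs three affected participants in a trial of three, so it cannot be met while anyone is unaffected

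*Protocol*

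**What the plan says.** Section 14.2 of the Protocol sets up three things for the NEI SAE Review Committee.

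- **Scheduled review:** "The Committee will review data on a semiannual basis to determine whether the study should continue".
- **Serious events:** "Should any suspected serious adverse reactions occur, the NEI CD may, at his discretion, assemble the Committee before the scheduled date".
- **Non-serious events:** the PI must report to the CD "if three or more participants experience non-serious suspected adverse reactions that require temporary or permanent cessation of the combination investigational treatment". The CD may then call the Committee together early to consider whether the whole study should cease.

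The sample size is the same wherever it is stated. Protocol 9.3 says "The accrual goal is three participants", and SAP 4.1 repeats it. Protocol 3.0 says "Three participants with severe ocular VHL disease who meet the eligibility criteria will receive the combination investigational treatment", and SAP 3.3 agrees. Participants who discontinue treatment are followed and analysed (Protocol 4.3). Neither document mentions replacing them or enrolling more than three.

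On timing, Protocol 4.1 states: "It is anticipated that all participants will be recruited within 12 months of activation". Under Protocol 4.3, dosing is every four weeks to Week 16 and then "every eight weeks through Week 48 (totaling nine treatments from baseline").

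**The concern.** A count-based trigger is useful if it can act while there is still someone to protect. Here the count equals the whole planned sample, so when the rule is met every participant has already had treatment interrupted or stopped. At that point it can inform only whether interrupted participants resume.

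Recruitment may be spread over 12 months. The first two participants could both have treatment ceased for non-serious suspected reactions, and the third could still be enrolled and dosed, without this rule requiring any report.

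This matters because safety is the primary outcome (Protocol 8.1) and because Protocol 1.7 states that E10030 has not been studied in eyes with ocular VHL disease. Treatment-interrupting reactions that are not serious are foreseeable: Section 7.0 singles out intraocular inflammation for monitoring at every visit.

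**Working it through.** The documents contain no power or error-rate calculation for this rule, so there is no computed figure to reproduce. The check compares the threshold with the accrual and then looks at timing.

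**Inputs**
- Threshold: at least 3 participants (Protocol 14.2).
- Accrual: 3 (Protocol 3.0, 9.3; SAP 3.3, 4.1).
- Treatment weeks: 0, 4, 8, 12, 16, 24, 32, 40, 48, which is 9 treatments of 2 injections each, or 18 injections (Protocol 4.3, Appendix 2).
- Recruitment: up to 12 months, about 52 weeks (Protocol 4.1).
- Review interval: semiannual (Protocol 14.2), taken here as 26 weeks.

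**Step 1: threshold as a share of accrual**

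| Rule | Share of three participants | Reachable with one participant unaffected? |
|---|---|---|
| Three or more (as written) | 3/3 = 100% | No |
| Two or more | 2/3 = 67% | Yes |
| One or more | 1/3 = 33% | Yes |

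If only two participants are treated, the written rule cannot be met. It counts participants rather than events, so repeated interruptions in one or two people do not meet it either.

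**Step 2: chance that the rule is met**

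The documents give no per-participant probability p of a non-serious treatment-stopping reaction, so p is an assumption, with participants taken as independent. For the written rule the probability is p³. For two or more it is 3p²(1−p) + p³. For one or more it is 1 − (1−p)³.

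| Assumed p | Three or more | Two or more | One or more |
|---|---|---|---|
| 0.1 | 0.001 | 0.028 | 0.271 |
| 0.3 | 0.027 | 0.216 | 0.657 |
| 0.5 | 0.125 | 0.500 | 0.875 |
| 0.7 | 0.343 | 0.784 | 0.973 |
| 0.9 | 0.729 | 0.972 | 0.999 |

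For the written rule to have an even chance of being met, p must be 0.5^(1/3) ≈ 0.79. This table is illustrative; the conclusion rests on Step 1 and needs no event rate.

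**Step 3: exposure between scheduled reviews**

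With visits at target weeks, the treatments falling in Weeks 0 to 26 are those at Weeks 0, 4, 8, 12, 16 and 24. That is 6 of 9 treatments, or 6 × 2 = 12 of 18 injections, for a participant who starts just after a review. If instead one participant is affected at baseline just after a review, another on the same schedule can receive the treatments at Weeks 4, 8, 12, 16 and 24 before the next review: 5 treatments, or 10 injections.

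**Step 4: staggered entry**

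The recruitment window (about 52 weeks) is longer than the dosing period (48 weeks). One participant's dosing can be finished before the third is enrolled.

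**Step 5: do other routes guarantee notice to the CD?**
- The early-meeting route for reactions in 14.2 covers serious ones only.
- Section 14.3 lets the Committee or IRB recommend stopping at any time, but they must first know of the events.
- Section 16.0 sends non-serious events to the IRB and CD within 14 days only if they are also unanticipated problems. Other non-serious AEs go to the Sponsor with no stated deadline and are summarised at Continuing Review.
- Sections 7.1 and 7.2 deal with individual discontinuation and state no duty to notify the CD.

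**The case against.** The strongest reply is that this clause is a reporting trigger, not a stopping rule, and that oversight does not hang on it. Convening is discretionary even at three, and nothing says the CD may convene only at three. Affected participants are already protected, because their treatment has by definition been stopped. The trial is small and single-centre, so the CD may well hear informally. The Coordinating Center advises the CD and passes on results of data checks (14.1, 15.0). Missed procedures go to the IRB within two weeks, and rates of missed events go regularly to the SAE Review Committee, on which the CD sits (4.5.1). A treatment-stopping drug reaction might often count as unanticipated, since Section 6.2 says no drug-specific adverse effects of E10030 have been identified in limited human use. Finally, three is called a goal; a fourth participant would make the rule reachable with one unaffected.

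Much of this stands as a limit on consequence. The exposure figures are upper bounds: they assume unlucky timing, no other communication, and that an earlier report would have changed dosing. How the Sponsor in 16.0 relates to the CD is not stated in the text reviewed, so that route may reach the CD in practice. A lower threshold would still leave convening to the CD's discretion.

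It does not rescue the threshold. The data-check and missed-procedure routes are not AE reports, the unanticipated-problem route is conditional, and over-enrolment is not provided for. None requires one or two such reactions to be reported to the CD, which is what a working version of this clause would do.

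**Conclusion.** The concern holds. At the stated accrual the rule needs 3 of 3 participants. It cannot prompt consideration of ceasing the study while any participant is unaffected, and it cannot be met at all if fewer than three are treated. This conclusion assumes only that accrual stops at three.

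The possible exposure of six of nine treatments between reviews further assumes a 26-week interval and visits on target, and is a ceiling rather than an expectation. The defect is confined to one supplementary escalation clause for non-serious reactions and alters no analysis. It should still be fixed, because safety is the primary outcome and this is the plan's only count-based study-level rule for such reactions.

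**What to change.** In Protocol 14.2, lower the threshold from three or more participants to one or more, or at most two or more. The choice belongs to the sponsor and the Committee. One or more gives the earliest notice but, because temporary cessation counts, could be met by a single deferred dose. Two or more avoids that and still leaves one participant unaffected when the rule is met.

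Section 14.2 gives no deadline for the PI's report. If prompt notice is wanted, a time limit could be added in the same sentence; Section 16.0 already uses 14 days for non-serious unanticipated problems.

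The cost is a one-line amendment and possibly one more PI report or Committee meeting. Visits, sample size and analyses are unchanged.

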14.3 Criteria for Stopping the Study

The NEI SAE Review Committee or IRB may recommend temporarily suspending or closing enrollment, or stopping the study at any time due to safety concerns, lack of efficacy or slow recruitment.

15.0 QUALITY ASSURANCE

The NEI and Emmes maintain quality control by adhering to standard operating procedures (NEI QA program and NEIS standard operating procedures). These procedures cover the full protocol cycle beginning with staff credentialing and training, and protocol development and

approval, through database development, data collection, monitoring and analysis and finally manuscript preparation at the conclusion of the study. Data quality assurance is of the utmost importance to the NEI and Emmes. The two groups use a quality assurance system that relies on real-time data checks and reports throughout the course of a study to ensure the accuracy of information. This system is a secure and confidential data management system that stores data and provides quality assurance and reporting. Emmes has developed a number of routine reports specifically designed for monitors (e.g., listings of SAEs, etc.).

Additionally, Emmes has developed summary reports of discrepancies, as well as reports of the exceptions databases, which include requests and reasons for exceptions. The results of the reports are communicated back to site staff, and, along with protocol compliance issues, to the DSMC (if applicable).

Following the monitoring plan for this study, Emmes will perform monitoring activities, including on-site audits, review of database entries and the resolution of study issues. In addition to monitoring, Emmes performs various detailed automated and manual data quality checks. The results from these checks and any protocol compliance issues are communicated back to site staff and to the NEI Project Officer, NEI CD and applicable regulatory bodies.

16.0 Reporting of Unanticipated Problems, Protocol Deviations and Adverse Events

The PI is responsible for detecting, documenting and reporting unanticipated problems, AEs, including SAEs and deviations in accordance with NIH policy, IRB requirements and federal regulations. Relatedness to the research of all SAEs will be determined by the PI in consultation with the NEI CD.

Serious unanticipated problems, SAEs (including deaths) that are not unanticipated problems and serious protocol deviations will be reported to the IRB and CD as soon as possible and in writing not more than seven days after the PI first learns of the event, unless immediate reporting is waived for specific SAEs as noted below. Not serious unanticipated problems and not serious deviations will be reported to the IRB and CD as soon as possible and in writing not more than 14 days after the PI first learns of the event. Written reports will be submitted in PTMS.

All AEs, deviations and unanticipated problems will be summarized and reported at the time of Continuing Review.

The PI will immediately report SAEs to the Sponsor according to the requirements of 21 CFR 312.64(b). The PI will record non-serious AEs and report them to the Sponsor.

Unexpected serious suspected adverse reactions will be reported to the FDA as soon as possible by facsimile or e-mail within seven days if life-threatening or resulting in death with a follow-up report within 15 days, and with a written report within 15 days otherwise.

All SAEs or unanticipated problems will be reported to Ophthotech Corp. as soon as possible.

17.0 ALTERNATIVES TO PARTICIPATION

Standard care for RCH in VHL ocular disease includes ablative therapies such as laser photocoagulation and trans-scleral cryotherapy. Other therapies include verteporfin photodynamic therapy, episcleral brachytherapy and external beam radiotherapy. Vitreoretinal surgery is used as an adjunct to ablative therapy in order to address vision-threatening epiretinal proliferation, tractional or rhegmatogenous retinal detachment or vitreous hemorrhage.

Participants may receive standard care treatment for RCH (laser photocoagulation and cryotherapy) and complications of RCH (vitreoretinal surgery) when indicated for significant clinical worsening during this study. If a participant achieves clinical improvement during the study that allows for standard care treatment that was not previously feasible, this treatment may be administered anytime starting at the Week 16 visit.

